11. STUDY TERMINATION

If more than 2 subjects in the investigational soft contact lens group develop serious expected (e.g., definite or probable MK) or unexpected device related adverse events, the study will be suspended. Upon review and consultation with IRB, DMC, and JJVC Safety Management Team , the study may be terminated.

The occurrence of one or more Unanticipated Serious Adverse Device Effect (USADE), or any SAE where the relationship to study agent cannot be ruled out, may result in stopping further dispensing of test article. In the event of a USADE or SAE, the Sponsor may unmask the treatment regimen for the subject(s) and will discuss this with the Investigator before any further subjects are enrolled.

The Sponsor will determine when a study will be stopped. The Principal Investigator always has the discretion to initiate stopping the study based on patient safety or if information indicates the study's results are compromised.

Clinical Study Protocol

Johnson & Johnson Vision Care, Inc.

JJVC reserves the right to terminate the study at any time for any reason. Additionally, the IEC/IRB reserves the right to terminate the study if an unreasonable risk is determined. The study can be terminated by the Principal Investigator at the individual clinical site due to specific clinical observations, if in their opinion, after a discussion with JJVC, it is determined that it would be unwise to continue at the clinical site.

JJVC (and the IEC/IRB and DMC, if applicable) will evaluate all adverse events. If it is determined that an adverse event presents an unreasonable risk, the investigation, or that part of the investigation presenting the risk, will be terminated as soon as possible.

Should the study be terminated (either prematurely or as scheduled), the Investigator will notify the IEC/IRB and Regulatory Authority as required by local regulatory requirements.

12. PROCEDURE FOR HANDLING PRODUCT QUALITY COMPLAINTS

A Product Quality Complaint (PQC) refers to any written, electronic, or oral communication that alleges deficiencies related to the identity, quality, durability, reliability, safety, effectiveness or performance of test articles after they have been released for clinical trial use.

Potential complaints may come from a variety of sources including but not limited to subjects, clinical research associates (CRA), clinical operations managers (COM), medical monitors, and site personnel, etc. The following are not considered product quality complaints:

- Subject satisfaction inquiries reported via “Subjective Questionnaires” and “Patient Reported Outcomes (PRO).”
- Clinical test articles that are stored improperly or damaged after receipt at the investigational site.
- Lens replacements that occur due to drops/fall-outs.
- Damage deemed by clinicians or clinical staff to be caused by handling by the user, and not indicative of a quality deficiency (i.e. tears, rips, etc.), only in situations where there is no deficiency alleged by the subject.

Within 24 hours of site personnel becoming aware that a PQC has occurred, the PQC must be recorded in the EDC system, which will trigger an automatic email notification to the appropriate COM/CRA and Clinical QA representative. In cases where the EDC system in use is not configured to send automatic notifications or when an EDC system is not used, the COM/CRA is responsible for notifying Clinical QA upon discovery that a PQC has occurred.

Upon receipt of the EDC notification, the COM/CRA will contact the study site to collect additional information which will include:

- Date the complaint was received/recorded in the EDC System (Date of Sponsor Awareness).
- Who received the complaint.

Clinical Study Protocol

Johnson & Johnson Vision Care, Inc.

- Study number.
- Clinical site information (contact name, site ID, telephone number).
- Lot number(s).
- Unique Subject Identifier(s).
- Indication of who first observed complaint (site personnel or subject).
- OD/OS indication, along with whether the lens was inserted.
- Any related AE number if applicable.
- Detailed complaint description (scheduled/unscheduled visit, wear time, symptoms, resolution of symptoms, etc.).
- Eye Care Provider objective (slit lamp) findings if applicable.
- Confirmation of product availability for return (and tracking information, if available), or rationale if product is not available for return
[REDACTED]

Once a complaint is received, it will be assessed by the COM, CRA, or trained site personnel to determine if it is an Adverse Event/Serious Adverse Event (AE/SAE). If the complaint results in an AE/SAE, the COM/CRA, or trained site personnel will follow section 13 of this protocol. If the AE/SAE was potentially the result of a product quality related deficiency, these procedures also applies and will be executed in parallel.

In some cases, a PQC form may be generated in EDC by the site in error. In this event, the PQC forms will be marked “Intentionally Left Blank” or “ILB”. Justification for ILB must be documented.

13. ADVERSE EVENTS

13.1. Definitions and Classifications

Adverse Event (AE) – An AE is “any untoward medical occurrence, unintended disease or injury, or untoward clinical signs (including abnormal laboratory findings) in subjects, users or other persons, whether or not related to the investigational medical device.”

Note: This definition includes events related to the investigational medical device or the comparator, and to the procedures involved. For users or other persons, this definition is restricted to events related to investigational medical devices.¹

An AE includes any condition (including a pre-existing condition) that:

1. Was not present prior to the study, but appeared or reappeared following initiation of the study.
2. Was present prior to the study but worsened during the study. This would include any condition resulting from concomitant illnesses, reactions to concomitant medications, or progression of disease states.

Note: Pregnancy must be documented as an adverse event and must be reported to the clinical monitor and to the Sponsor immediately upon learning of the event.

Clinical Study Protocol

Johnson & Johnson Vision Care, Inc.

Serious Adverse Event (SAE) – An SAE is any adverse event that led to any of the following:

- Death
- Serious deterioration in the health of the subject that resulted in any of the following:
- Life-threatening illness or injury
- Permanent or persistent impairment of a body structure or a body function
- Hospitalization or prolongation of patient hospitalization
- Medical or surgical intervention to prevent life-threatening illness or injury or permanent impairment to a body structure or a body function.
- Chronic disease
- Foetal distress, foetal death or a congenital physical or mental impairment of birth defect.

Diagnoses and conditions that are considered Ocular Serious Adverse Events include, but not limited to:

- Microbial Keratitis (MK)
- Iritis (including cells in the anterior chamber)
- Permanent decrease in best spectacle corrected visual acuity equivalent to 2 acuity lines or greater
- Central Corneal Opacity
- Central Corneal Neovascularization
- Uveitis
- Endophthalmitis
- Hypopyon
- Hyphemia
- Penetration of Bowman's Membrane
- Persistent Epithelial Defect
- Limbal cell Damage leading to Conjunctivalization

Significant Adverse Events – are defined as events that are symptomatic and warrant discontinuation (temporary or permanent) of the contact lens wear

Diagnoses and conditions that are considered Ocular Significant Adverse Events include, but not limited to the following:

- Contact Lens Induced Peripheral Ulcer (CLPU)
- Significant Infiltrative Events (SIE)
- Superior Epithelial Arcuate Lesions (SEALs)
- Any Temporary Loss of > 2 Lines of BSCVA
- Other grade 3 or higher corneal findings, such as abrasions or edema
- Non-contact lens related corneal events - e.g. Epidemic Keratoconjunctivitis (EKC)
- Asymptomatic Corneal Scar

Clinical Study Protocol

Johnson & Johnson Vision Care, Inc.

- Any corneal event which necessitates temporary lens discontinuation > 2 weeks

Non-Significant Adverse Events – are defined as those events that are usually asymptomatic and usually do not warrant discontinuation of contact lens wear but may cause a reduction in wear time. However, the Investigator may choose to prescribe treatment as a precautionary measure.

Diagnoses and conditions that are considered Ocular Non-Significant Adverse Events include, but not limited to the following:

- Non-significant Infiltrative Event (NSIE)
- Contact Lens Papillary Conjunctivitis (CLPC)
- Superficial Punctate Keratitis (SPK)
- Conjunctivitis: Bacterial, Viral, Allergic
- Blepharitis
- Meibomianitis
- Contact Dermatitis
- Localized Allergic Reactions
- Any corneal event not explicitly defined as serious or significant adverse event, which necessitates temporary lens discontinuation < 2 weeks

Adverse Device Effect (ADE) – An ADE is an “adverse event related to the use of an investigational medical device.”

- NOTE 1: This definition includes adverse events resulting from insufficient or inadequate instructions for use, deployment, implantation, installation, or operation, or any malfunction of the investigational medical device.
- NOTE 2: This definition includes any event resulting from use error or from intentional misuse of the investigational medical device.¹

Unanticipated Adverse Device Effect (UADE) – A UADE is any serious adverse effect on health or safety or any life-threatening problem or death caused by, or associated with, the test article, if that effect, problem, or death was not previously identified in nature, severity, or degree of incidence in the investigational plan, Investigator’s Brochure or protocol, or any other unanticipated serious problem associated with the test article that relates to the rights, safety and welfare of subjects.

13.2. Assessing Adverse Events

In conjunction with the medical monitor, the Investigator will evaluate adverse events to ensure the events are categorized correctly. Elements of categorization will include:

- Seriousness/Classifications (see definition in section 13.1).

Clinical Study Protocol

Johnson & Johnson Vision Care, Inc.

- Causality or Relatedness – i.e. the relationship between the test article, study treatment or study procedures and the adverse event (not related, unlikely related, possibly related, or related - see definition in section 13.2.1).
- Adverse Event Severity – Adverse event severity is used to assess the degree of intensity of the adverse event (mild, moderate, or severe - see definition in section 13.2.2).
- Outcome – not recovered or not resolved, recovering or resolving, recovered or resolved with sequelae, recovered or resolved, death related to adverse event, or unknown.
- Actions Taken – none, temporarily discontinued, permanently discontinued, or other.

13.2.1. Causality Assessment

Causality Assessment – A determination of the relationship between an adverse event and the test article. The test article relationship for each adverse event should be determined by the investigator using these explanations:

- Not Related- An adverse event that is not related to the use of the test article, study treatment or study procedures.
- Unlikely Related – An adverse event for which an alternative explanation is more likely, e.g. concomitant treatment, concomitant disease(s), or the relationship of time suggests that a causal relationship is not likely.
- Possibly Related – An adverse event that might be due to the use of the test article, or to the study treatment or study procedures. An alternative explanation, e.g. concomitant treatment, concomitant disease(s), is inconclusive. The relationship in time is reasonable. Therefore, the causal relationship cannot be excluded.
- Related – An adverse event that is listed as a possible adverse effect (device) or adverse reaction (drug) and cannot be reasonably explained by an alternative explanation, e.g. concomitant treatment or concomitant disease(s). The relationship in time is very suggestive, e.g. it is confirmed by de-challenge and re-challenge.

13.2.2. Severity Assessment

Severity Assessment – A qualitative assessment of the degree of intensity of an adverse event as determined by the Investigator or reported to him/her by the subject. The assessment of severity is made irrespective of test article, study treatment or study procedure relationship or seriousness of the event and should be evaluated according to the following scale:

- Mild – Event is noticeable to the subject but is easily tolerated and does not interfere with the subject's daily activities.
- Moderate – Event is bothersome, possible requiring additional therapy, and may interfere with the subject's daily activities.
- Severe – Event is intolerable, necessitates additional therapy or alteration of therapy and interferes with the subject's daily activities.

Clinical Study Protocol

Johnson & Johnson Vision Care, Inc.

13.3. Documentation and Follow-Up of Adverse Events

The recording and documenting of adverse events (ocular and non-ocular) begin when the subjects are exposed to the test article, study treatment or study procedure. Adverse events reported before the use of test article, start of study treatment, or study procedures will be recorded as medical history. However, if the condition deteriorates at any time during the study it will be recorded and reported as an AE. Untoward medical events reported after the subject's exit from the study will be recorded as adverse events at the discretion of the Investigator.

Upon finding an adverse event, the Principal Investigator will document the condition in the subject record and in the eCRFs and complete the Adverse Event eCRF.

Complete descriptions of all adverse events must be available in the subject record. All Adverse Events including local and systemic reactions not meeting the criteria for "serious adverse events" shall be captured on the appropriate case report form or electronic data system. All adverse events occurring while the subject is enrolled in the study must be documented appropriately regardless of relationship.

It is the Investigator's responsibility to maintain documentation of each reported adverse event. All adverse events will be followed in accordance with applicable licensing requirements. Such documentation will include the following:

- Adverse event (diagnosis not symptom).
- Drawings or photographs (where appropriate) that detail the finding (e.g., size, location, and depth, etc.).
- Date the clinical site was notified.
- Date and time of onset.
- Date and time of resolution.
- Adverse event classification, severity, and relationship to test articles, as applicable.
- Treatment regimen instituted (where appropriate), including concomitant medications prescribed, in accordance with applicable licensing requirements.
- Any referral to another health care provider if needed.
- Outcome, ocular damage (if any).
- Likely etiology.
- Best corrected visual acuity at the discovery of the event and upon conclusion of the event, if the AE is related to the visual system.

Upon discovery of an AE that is deemed 'possibly related' or 'related' to the test article or study procedures (whether related to the visual system or not), an AE review form [REDACTED] must be completed. Additional dated and initialed entries should be made at follow-up evaluations. Separate forms must be completed for each eye if the AE is bilateral.

In addition, if an infiltrate(s) is present, he/she will complete the Corneal Infiltrate Assessment eCRF. Where necessary, a culture of the corneal lesion will be collected to determine if the

Clinical Study Protocol

Johnson & Johnson Vision Care, Inc.

infection is microbial in nature. If cultures are collected, the date of culture collection and laboratory utilized will be recorded.

Changes in the severity of an AE shall be documented to allow an assessment of the duration of the event at each level of intensity to be performed. Adverse events characterized as intermittent require documentation of the onset and duration of each episode. Changes in the assessment of relationship to the Test Article shall also be clearly documented.

Subjects who present with an adverse event shall be followed by the Investigator, within licensure, until all signs and symptoms have returned to pre-treatment status, stabilized, or been satisfactorily resolved. If further treatment beyond licensure is required, the patient will be referred to the appropriate health care provider. The Investigator will use his/her clinical judgment as to whether a subject reporting with an adverse event will continue in the study. If a subject is discontinued from the study, it will be the responsibility of the Investigator to record the reason for discontinuation. The Investigator will also document the adverse event appropriately and complete the Adverse Event eCRF. Any subjects with ongoing adverse events related to the test article, study treatment or study procedures, as of the final study visit date, should be followed to resolution of the adverse event or until referral to an appropriate health care provider, as recommended by the Investigator. Non-ocular adverse events that are not related to the test article, study treatment, or study procedures may be recorded as "ongoing" without further follow-up.

13.4. Reporting Adverse Events

The Investigator will notify the Sponsor of an adverse event by e-mail, facsimile, or telephone as soon as possible and no later than 24 hours from discovery for any serious /significant adverse events, and 2 days from discovery for any non-significant adverse event. In addition, a written report will be submitted by the Principal Investigator to the IEC/IRB according to their requirements (section 13.4.2). The report will comment whether the adverse event was considered to be related to the test article, study treatment or study procedures.

13.4.1. Reporting Adverse Events to Sponsor

Serious/Significant Adverse Events

The Investigator will inform the sponsor of all serious/significant adverse events occurring during the study period as soon as possible by e-mail or telephone, but no later than 24 hours following discovery of the event. The Investigator is obligated to pursue and obtain information requested by the Sponsor in addition to that information reported on the eCRF. All subjects experiencing a serious/significant adverse event must be followed up and all outcomes must be reported.

When medically necessary, the Investigator may break the randomization code to determine the identity of the treatment that the subject received. The Sponsor and study monitor should be notified prior to unmasking the test articles.

In the event of a serious/significant adverse event, the Investigator must:

Clinical Study Protocol

Johnson & Johnson Vision Care, Inc.

- Notify the Sponsor immediately.
- Obtain and maintain in the subject's records all pertinent medical information and medical judgment for colleagues who assisted in the treatment and follow-up of the subject.
- Provide the Sponsor with a complete case history which includes a statement as to whether the event was or was not related to the use of the test article.
- Notify the IEC/IRB as required by the IEC/IRB reporting procedure according to national regulations.

Unanticipated (Serious) Adverse Device Effect (UADE)

In the event of an Unanticipated (Serious) Adverse Device Effect (UADE), the Investigator will submit a report of the UADE to the Sponsor and IEC/IRB as soon as possible, but no later than 24 hours after the Investigator first learns of the effect. This report is in addition to the immediate notification mentioned above.

The Sponsor must conduct an evaluation of the UADE and must report the results of the evaluation to FDA, the IEC/IRB and participating Investigators within 10 working days after the Sponsor first receives notification of the effect.

Non-Serious Adverse Events

All non-serious adverse events, including non-serious adverse device effects, will be reported to the sponsor by the Investigator no later than 2 days from discovery.

13.4.2. Reporting Adverse Events to the Responsible IEC/IRB and Health Authorities

Adverse events that meet the IEC/IRB requirements for reporting must be reported within the IEC/IRB's written guidelines. Each clinical site will refer to and follow any guidelines set forth by their Approving IEC/IRB. Each clinical site will refer to and follow any guidelines set forth by their local governing Health Authorities.

The Sponsor will report applicable Adverse Events to the local health authorities according to the written guidelines, including reporting timelines.

13.5. Event of Special Interest

None

13.6. Reporting of Pregnancy

Subjects reporting pregnancy (by self-report) during the study will be discontinued after the event is recorded as an Adverse Event. Once discontinued, pregnant participants and their fetuses will not be monitored for study related purposes. Pregnant participants are not discontinued from contact lens or solution related studies for safety concerns, but due to general concerns relating to pregnancy and contact lens use. Specifically, pregnant women are

Clinical Study Protocol

Johnson & Johnson Vision Care, Inc.

discontinued due to fluctuations in refractive error and/or visual acuity that occur secondary to systemic hormonal changes, and not due to unforeseen health risks to the mother or fetus.

14. STATISTICAL METHODS

14.1. General Considerations

Statistical Analysis will be undertaken by the sponsor or under the authority of the sponsor. A general description of the statistical methods to be implemented in this clinical trial is outlined below.

All data summaries and statistical analyses will be performed using the SAS software Version 9.4 or higher (SAS Institute, Cary, NC). Throughout the analysis of data, the results for each subject/eye will be used when available for summarization and statistical analysis. Unscheduled visits will be summarized separately and will be excluded from the statistical analysis.

Summary tables (descriptive statistics and/or frequency tables) will be provided for all baseline variables, efficacy variables and safety variables as appropriate. Continuous variables will be summarized with descriptive statistics (n, mean, standard deviation [SD], median, minimum and maximum). Frequency count and percentage of subjects or eyes within each category will be provided for categorical data.

14.2. Sample Size Justification

The plan is to enroll 115 subjects with a target completion of 100 subjects with approximately 50 subjects in the Test group and approximately 50 in the Control group. This is a feasibility study, and the sample size is chosen not based on estimates from historical studies with the product characteristics. The data collected for this study will be used to design future clinical trials. Thus, power calculations were conducted under different scenarios for the primary hypotheses to provide estimates on power with 2-sided type I error of 0.05 given the parallel design and 1:1 randomization ratio for average daily wear time and LogMAR visual acuity test at a 4-meter distance under high luminance/low contrast (HLLC) and low luminance/high contrast (LLHC) conditions.

Table 7 provides a summary of power based on the hypothesis of non-inferiority for logMAR visual acuity test at a 4-meter distance under either HLLC or LLHC at 1 Week Follow-up visit with a non-inferiority margin of 0.05 logMAR. Table 8 provides a summary of power based on the hypothesis of non-inferiority for average daily wear time at 1-week follow-up visit with a non-inferiority margin of 1 hour. The power calculation based on two sample t-test is conducted using the POWER procedure in SAS 9.4.

Clinical Study Protocol

Johnson & Johnson Vision Care, Inc.

Table 7: Power Calculation for the first primary hypothesis of logMAR visual acuity for either HLLC or LLHC at 2-week follow-up with a non-inferiority margin of 0.05.

Mean Difference (Test - Control)	Type I error	Standard Deviation	Total Sample Size (n/2 per arm)	Power
-0.01	0.05	0.08	100	0.981
-0.01	0.05	0.09	100	0.952
-0.01	0.05	0.10	100	0.909
0.00	0.05	0.08	100	0.928
0.00	0.05	0.09	100	0.867
0.00	0.05	0.10	100	0.799

As shown in the Table 7, the power is 0.8 or higher to show non-inferiority of the Test relative to the Control with respect to logMAR VA test at a 4-meter distance under either HLLC or LLHC when the Test - Control ≤ 0 and the standard deviation for both Test and Control < 0.10 .

Table 8: Power Calculation for the second primary hypothesis of average daily wear time at 2-week follow-up with a non-inferiority margin of 1.

Mean Difference (Test - Control)	Type I error	Standard Deviation	Total Sample Size (n/2 per arm)	Power
-0.05	0.05	1.90	100	0.799
-0.05	0.05	1.93	100	0.788
0.00	0.05	1.90	100	0.834
0.00	0.05	1.93	100	0.823
0.05	0.05	1.90	100	0.864
0.05	0.05	1.93	100	0.855

As shown in the Table 8, the power is 0.8 or higher to show non-inferiority of the Test relative to the Control with respect to when the Test - Control ≥ 0 and the standard deviation for both Test and Control ≤ 1.93 .

Clinical Study Protocol

Johnson & Johnson Vision Care, Inc.

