2.3. Hypotheses

This is a feasibility study and all the hypotheses are exploratory in nature.

Primary Hypotheses:

There are two co-primary hypotheses in this study. Both of them must be met to satisfy the primary objective of the study.

1. The Test lens will be non-inferior to the Control lens with respect to logMAR visual performance (using ETDRS visual acuity charts) at the 2-week follow-up visit. A non-inferiority margin of 0.05 logMAR will be used.
2. The Test lens will be non-inferior to the Control lens with respect to average daily wear time at 2-week follow-up visit. A non-inferiority margin of 1 hour will be used.

Secondary Hypotheses:

1. The Test lens will be non-inferior to the Control lens with respect to overall CLUE comfort score at the follow-up visit. A non-inferiority margin of -5 points will be used.
2. The Test lens will be non-inferior to the Control lens with respect to overall CLUE vision score at the follow-up visit. A non-inferiority margin of -5 points will be used.

All primary hypotheses of this study have to be met for study success.

Clinical Study Protocol

Johnson & Johnson Vision Care, Inc.

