14.4. Level of Statistical Significance

Since this is a feasibility study, the primary and secondary endpoints will be each tested under a Type I error rate of 5%. If exploratory statistical analysis is conducted after reviewing the descriptive summary of an endpoint, a type I error rate of 5% will be used with no multiplicity adjustments.

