14.5. Primary Analysis

The co-primary endpoints for this study are the logMAR VA test at a 4-meter distance under either HLLC or LLHC and the average daily wear time at 2-week follow-up evaluated after 14 ± 4 days of lens wear. The primary analysis will be conducted on per-protocol populations.

Visual Performance

Monocular distance visual performance in logMAR scale at follow-up visits will be analyzed using a mixed model of repeated measurement (MMRM) for HLLC and LLHC respectively to compare between Test and Control lenses at 2-week follow-up. The model will include baseline logMAR, lens type, visit, and the interaction of lens type and visit as the fixed effect, and investigational site and patient as random effects. Baseline demographics such as age and gender have historically limited influence on objective visual performance; thus, in accordance with the principle of parsimony, will not be included in the model. The covariance of residual errors between two follow-up visits across periods for the same eye and subject across wearing periods will be modeled using an unstructured (UN) covariance structure.

The null and alternative hypotheses for non-inferiority of Test lens relative to Control are as follows:

$$H_0: \Delta > 0.05$$
$$H_A: \Delta \leq 0.05$$

Clinical Study Protocol

Johnson & Johnson Vision Care, Inc.

where Δ is the mean difference in logMAR between Test lens and Control lens (Test minus Control) at 2-week follow-up. Non-inferiority will be declared if the upper bound of the confidence interval of the mean difference between Test and Control is less than 0.05.

Average Daily Wearing Time

Average daily wear time will be analyzed using a similar MMRM model with fixed and random effects described in the primary analysis. Age and gender will also be included as fixed effects.

The null and alternative hypotheses for non-inferiority of Test lens relative to Control are as follows:

$$H_0: \Delta < -1$$
$$H_A: \Delta \geq -1$$

where Δ is the mean difference in average daily wearing time between Test lens and Control lens (Test minus Control) at 2-week follow-up. Non-inferiority will be declared if the lower bound of the confidence interval of the mean difference between Test and Control is greater than -1.

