14.6. Secondary Analysis

CLUE Comfort and Vision scores

CLUE scores at follow-up visits will be analyzed using a MMRM model for comfort and vision respectively to compare between Test and Control lenses at 2-week follow-up. Each regression model will include the baseline score, lens type, visit, and the interaction of lens type and visit as fixed effects and investigational site as a random effect (G-side). Age and gender will also be included as fixed effects. The covariance of residual errors between different periods for the same subject will be modeled using an unstructured (UN) covariance structure. The Kenward and Roger method will be used for the calculation of the denominator degree of freedom.⁸

The null and alternative hypotheses for non-inferiority of Test lens relative to Control are as follows:

$$H_0: \Delta < -5$$
$$H_A: \Delta \geq -5$$

where Δ is the CLUE score mean difference between Test lens and Control lens (Test minus Control) at 2-week follow-up. The hypothesis will be tested via the corresponding two-sided 95% confidence interval (CI) for least squares mean (LSM) difference (Test - Control) in CLUE scores. Non-inferiority will be declared if the lower bound of the confidence interval of the mean difference between Test and Control is greater than -5.

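### The powers in Tables 7 and 8 hold only at one-sided 0.05, not at the 2-sided 0.05 stated in Section 14.2, and the primary tests have no stated confidence level

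*Combined protocol and SAP*

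**What the plan says.** Section 14.2 presents power scenarios that "provide estimates on power with 2-sided type I error of 0.05 given the parallel design". They are for a two-sample t-test in SAS PROC POWER with 100 completers, 50 per arm. The tables list the type I error as 0.05 with no sidedness. Two summary sentences follow.

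- Acuity: "As shown in the Table 7, the power is 0.8 or higher to show non-inferiority of the Test relative to the Control", for a Test minus Control difference of at most 0 and an SD below 0.10 logMAR.
- Wear time: "As shown in the Table 8, the power is 0.8 or higher to show non-inferiority of the Test relative to the Control", for a difference of at least 0 and an SD of at most 1.93 h.

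Section 14.4 says that "the primary and secondary endpoints will be each tested under a Type I error rate of 5" percent, without saying one-sided or two-sided.

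Section 14.5 gives the primary decision rules. For visual performance: "Non-inferiority will be declared if the upper bound of the confidence interval of the mean difference between Test and Control is less than 0.05". For wear time: "Non-inferiority will be declared if the lower bound of the confidence interval of the mean difference between Test and Control is greater than -1". Neither rule states the confidence level of the interval.

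Section 14.6 does name a level, a two-sided 95% interval, but it is written for the CLUE comfort and vision scores only.

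Section 2.3 makes the primary tests the success criterion: "All primary hypotheses of this study have to be met for study success".

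**The concern.** A non-inferiority claim uses one bound of the interval. A 2-sided type I error of 0.05 therefore means 0.025 in the direction that matters, and a 95% interval. If the printed powers were computed with 0.05 in that direction, they belong to a 90% interval, which is a looser test than the one Section 14.2 describes. Either the sidedness in the text or both power columns would be wrong.

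Two things are at stake. First, the plan would report power that the stated test does not have, in a study whose data are meant to inform the design of later trials. Second, and more important, Section 14.5 does not say which interval decides the study. If the level is chosen after the data are seen, the same result could be called a success or a failure.

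**Working it through.** **Inputs.** 50 completers per arm, 1:1 allocation, two-sample t-test (Section 14.2). Margins of 0.05 logMAR and 1 hour (Section 2.3). Differences (d) and SDs from Tables 7 and 8.

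**Formula.** Degrees of freedom = 2 × 50 − 2 = 98. SE = SD × √(2/50) = 0.2 × SD. Noncentrality = distance from margin / SE, where the distance is 0.05 − d for acuity and 1 + d for wear time. Power is the probability that a noncentral t on 98 degrees of freedom exceeds the critical value: 1.661 at one-sided 0.05, or 1.984 at one-sided 0.025.

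*Example:* Table 7, d = 0, SD 0.09. SE = 0.018 and noncentrality = 0.05/0.018 = 2.778. Power is 0.8673 at one-sided 0.05 and 0.7854 at one-sided 0.025. The plan prints 0.867.

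**All 12 rows.**

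| Table | d | SD | Noncentrality | Printed | One-sided 0.05 | One-sided 0.025 |
|---|---|---|---|---|---|---|
| 7 | −0.01 | 0.08 | 3.750 | 0.981 | 0.9812 | 0.960 |
| 7 | −0.01 | 0.09 | 3.333 | 0.952 | 0.9521 | 0.910 |
| 7 | −0.01 | 0.10 | 3.000 | 0.909 | 0.9090 | 0.844 |
| 7 | 0.00 | 0.08 | 3.125 | 0.928 | 0.9276 | 0.872 |
| 7 | 0.00 | 0.09 | 2.778 | 0.867 | 0.8673 | 0.785 |
| 7 | 0.00 | 0.10 | 2.500 | 0.799 | 0.7989 | 0.697 |
| 8 | −0.05 | 1.90 | 2.500 | 0.799 | 0.7989 | 0.697 |
| 8 | −0.05 | 1.93 | 2.461 | 0.788 | 0.7879 | 0.683 |
| 8 | 0.00 | 1.90 | 2.632 | 0.834 | 0.8336 | 0.741 |
| 8 | 0.00 | 1.93 | 2.591 | 0.823 | 0.8233 | 0.727 |
| 8 | 0.05 | 1.90 | 2.763 | 0.864 | 0.8641 | 0.781 |
| 8 | 0.05 | 1.93 | 2.720 | 0.855 | 0.8546 | 0.768 |

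One-sided 0.05 matches every row to three decimals; one-sided 0.025 matches none. A different sample size does not rescue the stated level. At one-sided 0.025 with 57 per arm (about half of the 115 enrolled), the last Table 7 row is 0.754, and with 100 per arm it is 0.940; the plan prints 0.799.

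**Size of the gap.** The smallest is 0.9812 − 0.9602 = 0.021 and the largest is 0.7879 − 0.6833 = 0.105.

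**The summary sentences at the stated level.** The wear-time sentence covers the four Table 8 rows with d ≥ 0, and all four fall below 0.80 (0.741, 0.727, 0.781, 0.768). The acuity sentence covers the four Table 7 rows with SD below 0.10, and one falls below 0.80 (d = 0, SD 0.09: 0.785).

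**SD that gives power 0.80 at zero difference.** At one-sided 0.05: 0.0998 logMAR and 1.997 h. At one-sided 0.025: 0.0884 logMAR and 1.767 h.

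**Where the two readings disagree.** The observed difference must clear the margin by the critical value times the SE.

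- Acuity, SD 0.09, SE 0.018: the limit is 0.05 − 1.661 × 0.018 = 0.0201 with a 90% interval and 0.05 − 1.984 × 0.018 = 0.0143 with a 95% interval. A result between +0.0143 and +0.0201 logMAR passes on the first and fails on the second.
- Wear time, SD 1.90, SE 0.38: the limits are −1 + 1.661 × 0.38 = −0.369 and −1 + 1.984 × 0.38 = −0.246. A result between about −0.37 and −0.25 h passes with 90% and fails with 95%.

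If the true difference is zero, the chance that the two readings disagree equals the power gap: 0.8673 − 0.7854 = 0.082 for acuity at SD 0.09, and 0.8336 − 0.7408 = 0.093 for wear time at SD 1.90.

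**The case against.** The strongest defence concerns weight. The plan calls this a feasibility study with exploratory hypotheses, and Section 14.2 says the sample size was not based on historical estimates. The powers are scenarios for a fixed number of subjects, so correcting them changes nothing for any subject. That is fair, and taken alone the tables would be a reporting correction. It does not reach the decision rule: Section 2.3 still sets a pass or fail criterion, and Section 14.5 leaves it without a confidence level.

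A second point is that the wording leans towards 95%. Section 14.2 says 2-sided, Section 14.4 puts primary and secondary endpoints under the same 5%, and Section 14.6 implements that 5% as a two-sided 95% interval. Only the back-calculated powers point to 90%. This makes 95% the more natural reading of the text, but it remains an inference, because Section 14.6 is written for CLUE scores. If it is right, all 12 printed powers are too high.

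Third, the planned primary analysis is a repeated-measures mixed model, with eye-level data for acuity, so its standard errors will differ from those of a two-sample t-test. This stands as a caveat. The ranges of disagreement above are approximations, and the recomputed powers match the plan's own power method rather than the mixed model. Some range of disagreement between a 90% and a 95% interval exists under any model.

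**Conclusion.** The concern holds. The stated basis of the power calculation and the printed powers are incompatible: 12 of 12 rows match one-sided 0.05 and none matches the stated 2-sided 0.05. At the stated level the powers fall by 2.1 to 10.5 points. The claim of 0.8 or higher then fails in all four wear-time rows it covers and in one of the four acuity rows. The level and sidedness of the two primary tests are not written anywhere in the plan, and this is the heavier part of the problem because study success depends on them.

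These figures rest on the plan's own method (two-sample t-test, 50 completers per arm, equal SDs). The observed differences at which the verdict changes are approximate for the planned mixed model.

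**What to change.** State the confidence level and sidedness of both primary tests in Sections 14.4 and 14.5 before unmasking, then make Section 14.2 agree by one of two routes.

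- **Two-sided 95% interval (one-sided 0.025).** Replace the power columns, in printed row order, with 0.960, 0.910, 0.844, 0.872, 0.785, 0.697 (Table 7) and 0.697, 0.683, 0.741, 0.727, 0.781, 0.768 (Table 8). Reword the two closing sentences: at zero difference, power of 0.8 or higher needs an SD of at most 0.088 logMAR or at most 1.76 h.
- **One-sided 0.05 (90% interval).** Keep both tables, change 2-sided to one-sided in Section 14.2, and name the 90% interval in Section 14.5.

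The cost is a few lines of protocol text, plus two table columns on the first route. That route reports less favourable power; the second openly makes the primary tests looser than the secondary ones. Neither requires a change in enrolment, since the sample size was not derived from these powers.
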